6.3.1 First Treatment Cycle

The first treatment cycle of the study will comprise two treatment groups as follows:

- Group A (active): BoNT/A-DP (20 units, 0.5 mL).
- Group B (placebo control): sterile, 0.9% sodium chloride (0.5 mL).

Eligible subjects will be randomized at baseline (day 0) to Group A or B to receive the first treatment in a 3:1 randomization scheme, respectively. Investigators and subjects will be blinded to the treatment administered and will evaluate the severity of glabellar lines independently. The subjects must perform their assessment independently and ideally before the investigator, to ensure they are not biased by the investigator. The same investigator must assess the subject at baseline and at the visits at weeks 1, 2 and 4 in the first treatment cycle.

After a screening period of up to 14 calendar days, subjects will receive the first treatment (BoNT/A-DP or placebo) and attend for visits at 1, 2 and 4 weeks after treatment and at 4-weekly intervals thereafter for evaluation of efficacy and safety (primary and key secondary efficacy endpoints will only be evaluated in the first treatment cycle in comparison with placebo). Re-screening will not be permitted.

The effect of botulinum toxin typically lasts a few months, hence the first treatment cycle will last at least 12 weeks and will end when the subjects qualify for re-treatment (in accordance with the "eligibility for re-treatment criteria" as outlined in Section 7.3). Efficacy duration of four to six months³⁶ or 17.1 ± 6.5 weeks³⁵ have been reported from other studies, hence the study is designed flexibly to adequately assess the duration of effect compared with placebo in the first treatment cycle.

6.3.2 Open Label Extension

After the first treatment cycle is completed, all subjects may enter the open label extension phase and will be dosed with BoNT/A-DP (20 U) for subsequent re-treatments.

Subjects will attend for visits at 1 and 4 weeks after re-treatment and at 4-weekly intervals thereafter. Additional telephone call follow-ups will take place in the open label extension phase two and eight weeks after each re-treatment. Each re-treatment cycle will last at least 12 weeks and will end when the subject qualifies for re-treatment (in accordance with the "eligibility for re-treatment criteria" as outlined in Section 7.3) or with the End of Study visit (see below). According to the study schedule (Section 2.2), a maximum of 4 treatments per subject (4 treatment cycles) is permitted during the study time frame, with treatments separated by a minimum of 12 weeks.

A subject may move to the next treatment cycle if more than 12 weeks have passed since the previous treatment. Starting at week 12 and at 4-weekly intervals thereafter, subjects will attend the site for the Evaluation for Re-treatment visit. If the subject has a FWS score (at maximum frown) of ≥ 2 , as determined by both the subject and the investigator, this visit on the same day at the same site visit will then be considered the End of Cycle visit and all other criteria required to determine eligibility for re-injection will be assessed e.g. negative urine pregnancy test (in women of child-bearing potential), lack of infection or inflammation in the planned injection area etc. Furthermore, all additional tests e.g. laboratory tests required for final cycle assessment will be performed (as outlined in the Schedule of events, Section 2.1). If the subject qualifies for re-treatment, on the same day at the same site visit, the

subject will then enter the next treatment cycle and will receive the next study drug treatment as part of the Re-Treatment visit (i.e. day 0 of the next treatment cycle).

If the FWS score (at maximum frown) is assessed as ≥ 2 by both the investigator and the subject, but the additional criteria for reinjection are not met, e.g. relevant infection or inflammation at the injection site, the subject may attend for a visit 4 weeks thereafter. Subjects with a positive pregnancy test, or subjects who do not agree to re-treatment, will be withdrawn from the study and the End of Study visit will be conducted at the earliest opportunity.

If at an Evaluation for Re-treatment visit the subject wants to get re-treated, but the investigator does not agree or vice versa (i.e. the FWS score is not \geq at least 2 by both assessments), the subject will return to the site 4 weeks thereafter for another Evaluation for Re-treatment visit. There is no limit to the number of Evaluation for Re-treatment visits. In order to consider a visit as the End of Cycle visit, there must always be agreement between investigator and subject on a FWS score (at maximum frown) of ≥ 2 .

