7.3 Eligibility Criteria for Re-treatment

The following criteria **MUST** be met for re-treatment:

- At time of re-treatment subject does not have relevant changes to their health status from enrollment, which would have prevented subject's entry into the study according to the inclusion and exclusion criteria.
- The subject must have been randomized to receive treatment and must have received at least one treatment (BoNT/A-DP or placebo).
- A minimum of 12 weeks must have elapsed since the previous study treatment.
- The subject's glabellar lines at maximum frown must have relapsed to a FWS score of 2 or 3 as determined by both the investigator and the subject.
- No relevant infection or inflammation in the planned injection area.
- Negative urine pregnancy test, in women of child-bearing potential.
- The subject must have received fewer than four study treatments.
- The subject must agree and consent to re-treatment.
- Re-treatment will be performed at the latest by week 48.

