
Visit 4 C1 Week 2
	
14 days ± 2 days after Baseline (Day 0)
	
Collect Subject Diary (Section 9.4) FWS Subject self-assessment (GLS-S, Section 10.1.1) FWS Investigator (GLS-I, Section 10.1.1) Full physical examination (Section 11.11) AE and AESI assessment (Section 11)¹³ Concomitant medication (Section 11.10.1) Photography (Section 10.1.2)¹²
	

Visit 5 C1
	
4 weeks ± 2 days after Baseline
	
FWS Subject self-assessment (GLS-S, Section 10.1.1) Modified Skindex-16 (GL-QoL) and FACE-Q
	

Week 4	(Day 0)	Appraisal of Lines Between Eyebrows and Age Appraisal VAS scales (Section 20) FACE-Q Satisfaction with Outcome Scale (Section 20.6) FWS Investigator (GLS-I, Section 10.1.1) Full physical examination (Section 11.11) AE and AESI assessment (Section 11) ¹³ Concomitant medication (Section 11.10.1) Photography (Section 10.1.2) Vital signs (Section 11.13) ECG (Section 11.16) Antibody test (Section 11.15.2) Clinical laboratory assessments (Section 11.15)	
Visit 6 C1 Week 8	8 weeks ± 2 days after Baseline (Day 0)	FWS Subject Self assessment (GLS-S, Section 10.1.1) FWS Investigator (GLS-I, Section 10.1.1) AE and AESI assessment (Section 11) ¹³ Concomitant medication (Section 11.10.1)	
Visit 7 (or 7a, 7b, 7c) Evaluation for re-treatment Visit ⁴ End Of Cycle ⁵ Second treatment - entry to open label extension	12 weeks ± 2 days after Baseline (Day 0), with possible extension at 4-weekly (± 2 days) intervals until subject is eligible for re-treatment	FWS Subject self-assessment (GLS-S, Section 10.1.1) FWS Investigator (GLS-I, Section 10.1.1) AE and AESI assessment (Section 11) ¹³ Concomitant medication (Section 11.10.1) Confirmation of eligibility for re-treatment (Section 7.3) Photography (Section 10.1.2) Urine pregnancy test (if applicable, Section 11.12) Vital signs (Section 11.13) ECG (Section 11.16) Clinical laboratory assessments (Section 11.15) Antibody test (Section 11.15.2) Modified Skindex-16 (GL-QoL) and FACE-Q Appraisal of Lines Between Eyebrows and Age Appraisal VAS scales (Section 20) FACE-Q Satisfaction with Outcome Scale (Section 20.6) Eligibility for re-treatment (Section 7.3) ⁶ <hr/> Consent for re-treatment SECOND TREATMENT - OPEN LABEL (Section 8.3) Post-treatment observation and AE assessment over 30 minutes	
Visit 8	1 week ± 2 days after	AE and AESI assessment (Section 11) ¹³ Concomitant medication (Section 11.10.1)	

C2 Week 1	second treatment	Full physical examination (Section 11.11)	

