³Inclusion and exclusion criteria to be re-confirmed at baseline include FWS for subject and investigator and concomitant medication.

⁴ At an Evaluation for Re-treatment visit (visits 7, 12 and 17), if the FWS score (at maximum frown) is not ≥ 2 , as determined by both the subject and the investigator, the subject will return at 4-weekly intervals thereafter until this criteria is met. The subsequent visit number for the cycle will remain the same, but will be amended with "a, b, c" etc., corresponding to the time extended (at 4 weekly intervals) in that treatment cycle, with each additional letter corresponding to a time point 4 weeks later in that cycle. For example, the first evaluation for re-treatment is at visit 7, week 12, however for subjects who are not eligible for re-treatment at week 12, but at week 16, this visit will be denoted "visit 7a", while "visit 7b" and "visit 7c" will denote visits at week 20 and week 24 in the first treatment cycle, respectively.

If the subject wants to get re-treated, but the investigator does not agree or vice versa (i.e. the FWS score is not ≥ 2 by both assessments), the subject will return to the site 4weeks thereafter for another Evaluation for Re-treatment visit.

⁵ Each treatment/re-treatment cycle will last at least 12 weeks. If more than 12 weeks have passed since the previous treatment and the subject has a FWS score (at maximum frown) of ≥ 2 , as determined by both the subject and the investigator, this visit will then be considered the End of Cycle visit and all other criteria required to determine eligibility for re-injection will be assessed.

⁶ If the subject qualifies for re-treatment (in accordance with the eligibility for re-treatment criteria) at the End of Cycle visit, the subject may then enter the next treatment cycle and will receive the next

study drug treatment. If the FWS score (at maximum frown) is assessed as ≥ 2 by both the investigator and the subject, but the additional criteria for reinjection are not met, e.g. presence of relevant infection or inflammation at the injection site, the subject will be allowed to return 4 weeks later for re-assessment .

⁷ Visits 9, 11, 14, 16, 19 and 21 will be telephone calls and will not require the subject to visit the site. If an AESI is reported, subjects must come to the site as soon as possible for an unscheduled visit, including a targeted physical examination to evaluate the AESI.

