6.6 DRM

For the DRM appropriate listings displaying all relevant data will be provided to the sponsor and serve as a source for the protocol deviations discussion about the classification into major and minor. No unblinding will be done for creation of these listings.

The following protocol deviations will be assessed on a case-by-case basis and a final decision on a possible exclusion from the PP will be done during the DRM:

- Inclusion/exclusion criteria violated
- Use of disallowed medications
- Serious breach of GCP
- Photography not collected or available for all visits
- Site staff performing the study assessment not trained
- Failure to discontinue subjects where appropriate.
- Subject re-treated despite not meeting all re-treatment eligibility criteria

Patients with minor protocol deviations will not be excluded from the PP.

Statistical Analysis Plan (SAP)

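### The re-treatment visit window and the two wordings of the minimum interval do not agree on days 82 to 84

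*Protocol*

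**What the plan says.** Three sets of statements bear on the earliest day of re-treatment.

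- **Inclusive wording.** Protocol 7.3, whose criteria are all mandatory, has "A minimum of 12 weeks must have elapsed since the previous study treatment". The synopsis carries the same criterion. Protocol 6.3.2 also describes the schedule as "with treatments separated by a minimum of 12 weeks", and SAP 3.3 repeats this.
- **Strict wording.** The next paragraph of Protocol 6.3.2 has "A subject may move to the next treatment cycle if more than 12 weeks have passed since the previous treatment", and SAP 3.3 carries the same sentence. Footnote 5 to Table 9-1 makes the End of Cycle visit depend on a similar condition, "If more than 12 weeks have passed since the previous treatment", although that footnote opens by saying that a cycle lasts at least 12 weeks.
- **Visit window.** Table 9-1 gives the timing of Visit 7, at which the second treatment is administered, as "12 weeks ± 2 days after Baseline (Day 0), with possible extension at 4-weekly (± 2 days) intervals until subject is eligible for re-treatment". Visits 12 and 17 have the same window after the second and third treatments. Protocol 6.3.5 allows two days either side for every visit except week 1 of the first cycle, and makes no exception for visits at which a dose is given.

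Protocol 2.1 (footnote 2) and 6.3.2 put evaluation, end of cycle and re-treatment on the same day. The notes in 2.1 measure time from the previous treatment.

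SAP 6.6 lists, among deviations judged case by case for exclusion from the Per-Protocol Analysis Set (PP), "Subject re-treated despite not meeting all re-treatment eligibility criteria".

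**The concern.** The minimum interval is a dosing rule that each site has to apply at up to three re-treatment visits per subject, in a trial planned for 700 subjects at about 18 sites. If the passages give different earliest days, a subject who attends on schedule may be re-treated at one site, sent away at another, and recorded as an eligibility breach at a third, with each site able to point to a passage that supports it.

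Three things depend on the answer: the spacing of toxin doses, the length of the treatment cycle for a subject who is turned away, and the set of re-treatments that the data review meeting treats as deviations. The PP is used for supporting analyses of the week 4 endpoint. A subject with valid week 4 data could therefore come up for exclusion because of a timing question that arises eight weeks later.

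**Working it through.** The documents give no figure to reproduce. The check is day arithmetic on the wordings.

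**Inputs.** 12 weeks = 12 × 7 = 84 days. The treatment day is day 0, as in Table 9-1. Days are counted as whole calendar days, which is an assumption.

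**Earliest day under each statement.**
- Visit window (Table 9-1, Protocol 6.3.5): 84 − 2 = day 82; latest day 84 + 2 = 86.
- Inclusive wording (Protocol 7.3, synopsis): day ≥ 84, so day 84.
- Strict wording (Protocol 6.3.2, Table 9-1 footnote 5, SAP 3.3): day > 84, so day 85.

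**Each day of the window against each statement.**

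| Day since last treatment | In visit window | Inclusive wording met | Strict wording met |
|---|---|---|---|
| 82 | yes | no | no |
| 83 | yes | no | no |
| 84 | yes | yes | no |
| 85 | yes | yes | yes |
| 86 | yes | yes | yes |

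The statements disagree on days 82, 83 and 84. The widest gap between earliest days is 85 − 82 = 3 days. On days 82 and 83 the conflict is between the schedule and both interval wordings. On day 84 it is between the two interval wordings themselves.

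**What follows for a subject turned away.** When the wrinkle score qualifies but another criterion is not met, Protocol 6.3.2 and Table 9-1 footnote 6 provide for a return four weeks later. Protocol 9.3.1 says that an unscheduled visit does not replace a scheduled one. No passage provides for a return one or two days later. If the four-week route is followed, re-treatment moves from about day 84 to about day 112, and 112 / 84 = 1.33, a cycle one third longer. This is the worst case.

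**What follows for the week 16 endpoint.** Under SAP 8.6.3 a subject re-treated before week 16 is a non-responder. A subject turned away at week 12 solely because of the interval has already been rated 2 or 3 by both raters. Without a new dose, that subject would ordinarily still be a non-responder at week 16, so the classification is normally the same either way. A difference arises if the deferred subject then misses the week 16 assessment, because the analysis of observed values would drop that subject instead of counting a non-response.

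**The case against.** The strongest reply is that the documents do contain a governing rule. Table 9-1 sends the eligibility check at Visit 7 to Section 7.3, and 6.3.1 and 6.3.2 end each cycle by reference to that section. Protocol 2.1 (footnote 2) and 4.5.1.2 give week 12 as the earliest time, and 6.3.3 refers to 12 or more weeks. The strict sentence in 6.3.2 is followed at once by one that starts evaluation at week 12. Read together, the strict wording looks like loose drafting, since taken literally it would bar re-treatment on the nominal visit day. A site can also avoid the problem by booking day 85 or 86, which satisfies every passage.

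Much of this stands. A reader might infer that there are three competing eligibility rules, so that a subject seen on day 82 or 83 is eligible under one of them. The documents do not support that: the window governs when a visit is on schedule, and no passage makes that subject eligible. A reader might also turn the three disputed days out of five into a share of visits or subjects. The documents give no distribution of visit days, so that count says nothing about how many would be affected.

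The consequences are also limited. Exclusion under SAP 6.6 is decided case by case, PP analyses are exploratory under SAP 8.6.1.1, and analyses are by visit regardless of window deviations.

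The reply does not remove the inconsistency. The strict wording appears in three operative places, one of them the footnote that defines the End of Cycle visit, and no passage says which wording prevails on day 84. The window for a dosing visit still extends two days below the minimum in 7.3, with no note that re-treatment cannot be given on those days.

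**Conclusion.** The inconsistency is real and lies in operative text. On days 82 and 83 a visit is on schedule but cannot meet the mandatory criterion. On day 84 the two interval wordings give opposite answers. The span is at most three days, counting whole days from treatment.

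It can affect dose spacing, deferral of an on-schedule subject (by four weeks at worst, a cycle one third longer) and the list of re-treatments reviewed for possible PP exclusion. How many subjects would be affected cannot be estimated from the documents.

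A reader might infer that efficacy conclusions are at risk. They are not: the week 4 primary analysis on the Full Analysis Set, the sample size and the error rate are untouched. The effect on the week 16 endpoint is little or none, given that deferred subjects have already relapsed. The point should be corrected because the rule governs dosing and the correction is cheap, not because it threatens the main result.

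**What to change.** Reconcile Protocol 6.3.2, 6.3.5, 7.3, Table 9-1 (Visits 7, 12 and 17, and footnote 5) and SAP 3.3 to a single interval rule, with a visit window for re-treatment that matches it. Carry any change through to the synopsis and the schedule notes. Cite that rule in SAP 6.6 as the definition of a re-treatment timing deviation, before unblinding, so that the data review meeting applies one standard. The sponsor must decide which interval applies; this review takes no position on it.

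The cost is a wording amendment to the protocol, the corresponding edit to the SAP and a note to sites. No change to sample size, data collection or the analysis methods is needed.

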6.3.3 End of Study Visit

The End of Study visit can take place in four-weekly intervals from study-week 48 until study-week 60. The last study drug re-treatment will be administered no later than week 48. For subjects receiving a re-treatment at week 48, the last cycle will end 12 weeks later at week 60 (i.e. End of Study visit).

The End of Study visit will take place at week 48, if the week 48 visit is an Evaluation for Re-treatment visit and the subject does not meet the criteria for re-treatment i.e. this visit is 12 or more weeks after the last treatment. As week 48 is the last possible time point for re-treatment, such subjects will continue with all additional assessments of the End of Study visit on the same day. For subjects having received their last injection 8 weeks or less prior to week 48, the End of Study visit will take place 12 weeks after the last study drug treatment was given, e.g. week 52 if the subject was re-treated at week 40.

For subjects who are prematurely discontinued from the study (at any time), the End of Study visit will take place within 1 week of discontinuation.

The number of treatments administered per subject will depend on the subject's qualification for re-treatment. A maximum of four study treatments may be administered per subject, with the last opportunity for re-treatment being week 48. A

subject will be followed-up until he/she would qualify for re-treatment (if below 48 weeks), since there is no maximum time frame for re-treatment.

6.3.4 Numbering of Visits

Visit numbers correspond with specific treatment and assessments as outlined in the Schedule of Events, Section 2.1. If subjects are not eligible for re-treatment at the "Evaluation for Re-treatment" visit, they will return at 4-weekly intervals thereafter, until they are eligible for treatment. The subsequent visit number for the cycle will remain the same, but will be amended with "a, b, c" etc., corresponding to the time extended (at 4-weekly intervals) in that treatment cycle. For example, the first evaluation for re-treatment is at visit 7, week 12; however for subjects who are not eligible at week 12, but at week 16, this visit will be denoted visit "7a", while "visit 7b" will denote week 20 in the first cycle and "visit 7c" will denote week 24 etc., with each additional letter corresponding to a time point 4 weeks later in that cycle. This approach will enable the visit numbers to be standardized, while allowing flexibility to assess the duration of efficacy in the first treatment cycle and in the open label extension.

6.3.5 Allowed Time Deviations Per Visit

A time deviation of ± 2 days is allowed for each visit (including telephone visits), except for the week 1 visit in the first treatment cycle, where a time deviation of ± 1 day is permitted. Sites must adhere to the schedule of events and visit windows and subjects must ensure they are available for those visits. However, if for practical reasons, e.g. bank holidays, a visit window cannot be met, a visit can be scheduled as close as possible to that visit window. However, any deviation from the visit schedule and its associated time windows will still be documented as a protocol deviation.

6.3.6 Duration of Study Period and Subject Participation

Subjects will participate in this study for a duration of 50 to 62 weeks from signing the informed consent form (ICF) to the End of Study visit (i.e. up to 14 calendar days for screening, followed by 48 to 60 weeks study participation).

Subjects will receive a maximum of four permitted rounds of treatment, with a minimum interval between treatments of 12 weeks.

6.4 Outcome Measures

6.4.1 Primary Outcome Measure

6.4.1.1 Efficacy

The primary efficacy endpoint is the proportion of subjects among BoNT/A-DP and placebo groups with a FWS score of 0 or 1 and an improvement ≥ 2 points in FWS score (at maximum frown) at the week 4 visit (of the first treatment cycle) relative to baseline (responders), based on both the investigator's and the subject's in-clinic assessments. Thus, the primary endpoint is a composite endpoint comprising investigator and subject assessments of treatment effectiveness.

6.4.2 Secondary Outcome Measures

6.4.2.1 Key Secondary Efficacy Endpoints

1. The percentage of responders at maximum frown (as defined in 6.4.1.1) at week 12 (after the first treatment with BoNT/A-DP or placebo).
2. The percentage of responders at week 16 (after the first treatment).
3. The proportion of subjects with a ≥ 1 point reduction in FWS score at rest at week 4 in the first treatment cycle, based separately on the investigators' and the subjects' in-clinic assessments (applicable only for subjects who have a FWS score at rest ≥ 1 at baseline).
4. The percentage of responders at week 20 or later (after the first treatment).
5. The extent of change in psychological impact (emotional and social functioning and concerns relating to their glabellar lines) at week 4 after the first treatment, in the BoNT/A-DP group in comparison with placebo, relative to baseline, as assessed by the modified Skindex-16 (Glabellar Line Quality of Life Scale [GL-QoL]) and the FACE-Q (Appraisal of Lines Between Eyebrows and Age Appraisal visual analog scales (VAS)), respectively.

